5. STUDY CONDUCT

5.1 Restrictions during the study

The following restrictions will apply to patients during both Part A and Part B of the study unless otherwise specified.

Contraception

Female patients of childbearing potential and their partners, who are sexually active, must agree to the use of 2 highly effective forms of contraception in combination throughout the period of taking study treatment and for at least 1 month after last dose of study drug. Male patients and their partners, who are sexually active and of childbearing potential, must agree to the use of 2 highly effective forms of contraception in combination, throughout the period of taking study treatment and for 3 months after last dose of study drug. Reliable methods of contraception should be used consistently and correctly; acceptable methods include barrier methods, implants, injectables, combined oral contraceptive methods, some IUDs, sexual abstinence or vasectomised partner. See [Appendix F](#) for details of acceptable birth control methods to be used within the study.

Concomitant medications

For restrictions regarding concomitant medications, please see Section 5.6.

Other restrictions

Patients will be required to fast for 4 hours prior to admission to the clinic at the screening visit.

In Part A, patients will be fasted from 1 hour before their olaparib dose until 2 hours after dosing. Water can be allowed as desired except for 1 hour before and after olaparib administration, excluding the water required to take the olaparib dose. In Part B, the olaparib may be taken with a light meal or snack.

In Part A, patients should not consume any grapefruit, grapefruit juice or grapefruit containing products from 48 hours before dosing until 96 hours post-dose.

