5.6 Concomitant and post-study treatment(s)

5.6.1 Restrictions for patients with hepatic impairment

In Part A, patients with hepatic impairment are required to refrain from taking cholestyramine/colestipol and ranitidine/nizatidine within 10 hours before and 10 hours after dosing with olaparib.

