5.6.2.1 Effect of other drugs on olaparib

CYP3A4/5 are the isozymes predominantly responsible for the metabolic clearance of olaparib. Clinical studies to evaluate the impact of known CYP3A inhibitors and inducers have shown that co-administration of a potent CYP3A inhibitor increased olaparib C_{max} 1.42-fold (90% CI: 1.33-1.52) and increased mean AUC 2.70-fold (90% CI: 2.44-2.97) and that co-administration of a potent CYP inducer decreased C_{max} by 71% (treatment ratio: 0.29; 90% CI: 0.24-0.33) and mean AUC by 87% (treatment ratio: 0.13; 90% CI: 0.11-0.16). It is therefore recommended that known strong inhibitors (eg, itraconazole, telithromycin, clarithromycin, boosted protease inhibitors, indinavir, saquinavir, nelfinavir, boceprevir and telaprevir) or inducers (eg, phenobarbitone, phenytoin, rifampicin, rifabutin, rifapentine, carbamazepine, nevirapine and St John's Wort) of these isozymes should be avoided with olaparib.

For patients taking strong inhibitors, the required washout period prior to starting olaparib is 2 weeks. For patients taking strong inducers, the required washout periods prior to starting olaparib in Part A are:

- Phenobarbitone, 5 weeks
- For any of the others, 4 weeks.

If the use of any potent inducers or inhibitors of CYP3A4 are considered necessary for the patient's safety and welfare during Part B, the investigator must contact the AstraZeneca Physician or their designated Medical Monitor. A decision to allow the patient to continue in the study will be made on a case-by-case basis.

Long term use of potent inducers and inhibitors of CYP3A4 should be avoided. If a decision is made to allow patients to use a potent inducer or inhibitor then they must be monitored carefully for any change in efficacy or safety of olaparib.

In vitro olaparib is a substrate for the efflux transporter Pgp. Clinical studies to evaluate the impact of known Pgp inhibitors and inducers have not been conducted. It is possible that olaparib may cause clinically relevant drug interactions with substrates of Pgp.

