5.6.3 Other concomitant medications

Any medications, with the exceptions noted in Section 5.7 below, which are considered necessary for the patient's welfare, and which are believed will not interfere with the IP, may be given at the discretion of the investigator, providing the medications, the doses, dates, and reasons for administration are recorded in the CRF.

In addition, any unplanned diagnostic, therapeutic, or surgical procedure performed during the study period must be recorded in the comments section of the corresponding AE report.

Anticoagulant therapy: Patients with normal hepatic function who are taking warfarin may participate in this study; however, it is recommended that prothrombin time (international normalised ratio [INR] and activated partial thromboplastin time [aPTT]) be monitored carefully at least once per week for the first month, then monthly if the INR is stable. Subcutaneous heparin is permitted for those patients with normal or impaired hepatic function.

Anti-emetics/anti-diarrhoeals: Prophylactic anti-emetics and/or anti-diarrhoeals will not be routinely given. Should a patient develop nausea, vomiting, and/or diarrhoea, which, in the investigator's opinion, is considered related to the IP, then appropriate treatment may be given.

Leukopenia and/or anaemia treatment: The use of colony-stimulating factors (CSFs) (eg, granulocyte-CSF [G-CSF], or granulocyte-macrophage CSF [GM-CSF]) should be managed as deemed appropriate by the investigator for the treatment of haematological AEs during Part B of the study (see Section 5.10).

The reason(s) for use, doses, and dates of treatment should be recorded in the patient's medical records and appropriate section of the CRF.

All medications (prescriptions or over-the-counter medications) present at the start of the study or started during the study or until 30 days from the end of the last protocol treatment and different from the IP must be documented in the CRF.

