11.7 Calculation or derivation of health economic variables (Not applicable)

12. STATISTICAL METHODS AND SAMPLE SIZE DETERMINATION BY ASTRAZENECA OR DELEGATE

12.1 Description of analysis sets

The study physician, pharmacokineticist, and statistician will agree on the strategy for dealing with data affected by protocol deviations before any formal statistical analysis is performed.

The analysis sets are defined in [Table 11](#).

Table 11 **Definition of analysis sets**

Analysis Set	Population
PK analysis set	All patients who receive an olaparib dose and have full PK sampling up to 96 hours post-dose.
Evaluable for Safety	All patients who receive at least 1 dose of olaparib and for whom any post-dose data are available will be included in the safety population

If a patient has a major protocol deviation that affects the evaluability of the PK profile, then the patient will not form part of the PK analysis set.

Major protocol deviations include changes to the procedures that may impact the quality of the data, or any circumstances that can alter the evaluation of the PK. Examples include, but may not be limited to, vomiting following oral dosing occurring within the time frame of 2 times the median t_{max} , sample processing errors that lead to inaccurate bioanalytical results, incomplete dose administered, incomplete PK profile collected, and/or use of disallowed concomitant medication. In the case of a major protocol deviation, affected PK data collected will be excluded from the summaries and statistical analyses, but will still be reported in the study result listings. Major deviations will be listed and summarised in the CSR.

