- If, at a given time point, 50% or less of the plasma concentrations are NQ, the mean, SD, geometric mean, %CV, and %GCV will be calculated by substituting the limit of quantification (LOQ) for values which are NQ.
- If more than 50%, but not all, of the concentrations are NQ, the mean, geometric mean, SD, %CV, and %GCV will be reported as not calculable (NC).
- If all the concentrations are NQ, the geometric mean and mean will be reported as NQ and the SD, %CV, and %GCV as NC.

The PK parameters will be rounded for reporting purposes both in the summary tables and by-patient listings. For the calculation of descriptive statistics and the statistical analysis, rounded values as presented in the data listings will be used. Except for raw measurements (such as C_{\max} and t_{\max}), all other derived PK parameters will be reported to 3 significant digits.

The PK data will be presented by hepatic function group (moderate hepatic impairment, mild hepatic impairment or normal hepatic function).

The goal of the statistical analysis in Part A is to estimate the effect of hepatic function on the PK of olaparib. Following log-transformation, C_{\max} and AUC (or AUC_{0-t} , if AUC is not adequately estimable) of olaparib will be separately analysed by analysis of variance (ANOVA), fitting a term for hepatic function group (moderate hepatic impairment, mild hepatic impairment or normal hepatic function).

The analysis will be carried out to compare the ratio of geometric means (gmeans) of the following groups:

1. Child-Pugh A classified patients (mild hepatic impairment) compared to patients with normal hepatic function (controls).
2. Child-Pugh B classified patients (moderate hepatic impairment) compared to patients with normal hepatic function (controls).

The results of these analyses will be presented in terms of geometric means for each hepatic function group. The ratio of geometric means of each hepatically impaired group compared to the normal group (mild/moderate: controls) will be presented with the respective 1-sided 95% upper confidence limit.

The possibility that hepatic impairment has a clinically relevant effect on the exposure of olaparib will be considered if the upper 1-sided 95% confidence limit for the ratio does not lie below the limit of 2, where the limit of 2 implies a doubling in exposure.

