Laboratory data (clinical chemistry, haematology, and urinalysis) will be summarised and listed. Shift tables will be provided for select tests, where shift from baseline to the worst value within each part of the study and overall will be summarised. Laboratory data outside the reference ranges should be indicated in the listings.

Concomitant medications will be summarised by the coded terms. The number of patients receiving a medication will be summarised overall and for each part of the study. A medication taken during the course of the study is considered concomitant. A patient is only counted once if receiving the medication more than once.

The remaining safety variables will be presented using summary statistics for quantitative data and frequency counts for qualitative parameters.

All data will be summarised and listed appropriately.

The impact of any major protocol deviations, missing data, and the use of rescue or concomitant medication on the robustness of study results will be investigated and any methods employed to deal with these will be documented.

Additional tables, figures, or listings may be produced to aid interpretation.

Further details of summaries of the safety data will be given in the SAP.

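### Section 5.6.1 bars bile-acid resins and two H2 blockers around the Part A dose in impaired patients only; the same rule should cover controls (minor)

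*Protocol*

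**What the plan says.** Section 5.6.1 is titled as a set of restrictions for patients with hepatic impairment. For Part A it says that "patients with hepatic impairment are required to refrain from taking cholestyramine/colestipol and ranitidine/nizatidine within 10 hours before and 10 hours after dosing". No other section names these drugs for patients with normal hepatic function.

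Several other Part A rules bind every group:

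- Fasting (section 5.1): "In Part A, patients will be fasted from 1 hour before their olaparib dose until 2 hours after dosing".
- Grapefruit (section 5.1): "In Part A, patients should not consume any grapefruit, grapefruit juice or grapefruit containing products from 48 hours before dosing until 96 hours post-dose".
- CYP3A4 washout (section 5.6.2.1): "For patients taking strong inhibitors, the required washout period prior to starting olaparib is 2 weeks", with longer periods for strong inducers.

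Some medication rules do differ by group. Exclusion 22 (recent dose changes and disallowed co-medication) and exclusion 27 (warfarin and related coumarins) apply only to impaired patients. Section 5.6.3 lets controls take warfarin.

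For drugs not otherwise restricted, section 5.6.3 says that those "which are believed will not interfere with the IP, may be given at the discretion of the investigator". The primary analysis in section 12.2.2 is an ANOVA of log AUC and log Cmax "fitting a term for hepatic function group". It reports the ratio of each impaired group to controls.

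**The concern.** The window in section 5.6.1 is tied to the olaparib dose and applies in Part A, the only part in which pharmacokinetics are measured. That placement suggests a rule meant to protect the PK profile, although the protocol does not say so. If so, nothing in the document explains why it should matter on only one side of the comparison.

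The study is non-randomised, with 8 evaluable patients per group, and the model has no term other than hepatic group. Any effect of these drugs on olaparib in controls would therefore be confounded with hepatic function. The control group is shared, so such an effect would enter the mild and the moderate ratio alike. Lower exposure in the controls concerned would inflate both ratios. Higher exposure would deflate them and make a true doubling easier to miss.

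**Working it through.** **1. Does another rule close the gap for controls?**

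- Inclusion 14 requires a stable regimen. A control on stable ranitidine meets it.
- The CYP3A4 washout in section 5.6.2.1 lists strong inhibitors and inducers. None of the four drugs is among its examples.
- Exclusion 22 covers impaired patients only.
- Section 5.6.3 relies on each investigator's belief about interference, across approximately 20 sites.
- Section 12.1 gives use of disallowed medication as an example of a major deviation, but these drugs are not disallowed for controls. The broader wording there, "any circumstances that can alter the evaluation of the PK", could reach such a case only by judgement.
- Section 12.2.3 promises that the impact of "the use of rescue or concomitant medication on the robustness of study results will be investigated". It names no method and stands in the safety section.

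So partial safeguards exist, but none sets the same rule for both sides of the ratio.

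**2. The plan's own figure.** Inputs from section 12.3: SD of log AUC 0.531, 8 per group, one-sided 95% limit. The limit for the ratio is 2 (section 12.2.2).

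- SE of the log ratio = 0.531 × √(1/8 + 1/8) = 0.2655.
- Non-centrality at a true ratio of 1 = ln 2 / 0.2655 = 0.6931 / 0.2655 = 2.611.
- Non-central t power: 79.9% with 14 df (two groups), 81.1% with 21 df (three-group ANOVA, critical t = 1.721).

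The stated figure of approximately 80% is reproduced. The steps below use 21 df.

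**3. How large would an interaction have to be?** The protocol gives neither the number of controls taking these drugs (k) nor the factor by which their AUC would change (m). Both are assumptions, and so is the 5% benchmark. If k of 8 controls have AUC multiplied by m, the impaired-to-control ratio is multiplied by m^(−k/8).

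| Shift in ratio | m, k = 1 | m, k = 2 | Consequence |
|---|---|---|---|
| × 1.05 | 1.05^(−8) = 0.677 (32% fall) | 1.05^(−4) = 0.823 (18% fall) | Chance of excluding a doubling at true ratio 1: 81.1% → 75.9% |
| ÷ 1.05 | 1.05^8 = 1.477 (48% rise) | 1.05^4 = 1.216 (22% rise) | Chance of wrongly excluding a true doubling: 5.0% → 7.1% |

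On the log scale the shift is ln 1.05 = 0.049, which is 0.049 / 0.2655 = 0.18 of a standard error. Smaller interactions do less, and no use by controls gives no shift at all.

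**4. Precision if exposed controls are left out.** With 8 impaired patients and 7 or 6 controls (20 or 19 df in the three-group model):

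- 7 controls: SE = 0.531 × √(1/8 + 1/7) = 0.2748, up 3.5%; power 78.5%.
- 6 controls: SE = 0.531 × √(1/8 + 1/6) = 0.2868, up 8.0%; power 75.3%.

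**The case against.** The strongest reply is that no defect has been shown. Section 5.6.1 is clear and nothing in the protocol contradicts it. The protocol reports no effect of these drugs on olaparib and does not indicate that any control takes them. An investigator who believes they interfere may not give them to a control under section 5.6.3, and if they do not interfere there is no bias. The gap is thus confined to an interaction that the investigator does not recognise. This stands as a limit on the size of the point. It does not make the rule equal, because judgement at each site is not a common restriction.

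A reader might infer that section 5.6.1 is a lone departure from otherwise uniform medication rules. The documents do not support that: exclusions 22 and 27 and the warfarin provision in section 5.6.3 also differ by group.

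A reader might also infer that the primary ratios are biased. That is not supported either, since both the existence and the direction of any effect are unknown. The percentages above show what would be needed and do not estimate what will happen.

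Two practical objections hold as well. Controls are recruited before the moderate group, and this version incorporates an amendment of March 2016 with Part A due to finish in Q3 2016, so a wording change may reach few of them and could leave controls under two rules. Section 5.6.3 asks for dates of concomitant drugs but not clock times, so a 10-hour window cannot be reliably rebuilt for controls already dosed.

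**Conclusion.** The point holds as a minor one. The restriction binds impaired patients only, and controls, who form the denominator of both primary ratios, are covered only by investigator judgement. The protocol states no reason for this.

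The size of any bias cannot be derived from the document and may be zero. Under the stated SD and 8 per group, a single control would need an AUC change of about a third downwards or a half upwards to move the ratio by 5%. The planned power and sample size are unaffected. What justifies acting is the low cost of making the rule equal, not any demonstrated harm.

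**What to change.** In section 5.6.1, make all patients the subject of the restriction in place of those with hepatic impairment, and retitle the section. Both sides of the ratio then follow the same rule.

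The cost is a one-line change and a 20-hour pause (10 hours before plus 10 after) in these drugs for any control taking them. Where possible, patients are already resident from the evening of Day -1 until 24 hours after the dose, so sites can apply it with little extra work. It reaches only controls not yet dosed.

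For controls already dosed, flag any recorded use of these drugs on the day before or the day of dosing. This is coarser than the 10-hour window but can be done from the dates that must be recorded. If there is any such use, repeat the AUC and Cmax ratios without those patients. Because leaving out one or two controls loses precision, this should be a supportive check and should not replace the main analysis.

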5.6.2 Olaparib and CYP3A4

The use of any natural/herbal products or other traditional remedies should be discouraged, but use of these products, as well as use of all vitamins, nutritional supplements, and all other concomitant medications must be recorded in the case report form (CRF).

5.6.2.1 Effect of other drugs on olaparib

CYP3A4/5 are the isozymes predominantly responsible for the metabolic clearance of olaparib. Clinical studies to evaluate the impact of known CYP3A inhibitors and inducers have shown that co-administration of a potent CYP3A inhibitor increased olaparib C_{max} 1.42-fold (90% CI: 1.33-1.52) and increased mean AUC 2.70-fold (90% CI: 2.44-2.97) and that co-administration of a potent CYP inducer decreased C_{max} by 71% (treatment ratio: 0.29; 90% CI: 0.24-0.33) and mean AUC by 87% (treatment ratio: 0.13; 90% CI: 0.11-0.16). It is therefore recommended that known strong inhibitors (eg, itraconazole, telithromycin, clarithromycin, boosted protease inhibitors, indinavir, saquinavir, nelfinavir, boceprevir and telaprevir) or inducers (eg, phenobarbitone, phenytoin, rifampicin, rifabutin, rifapentine, carbamazepine, nevirapine and St John's Wort) of these isozymes should be avoided with olaparib.

For patients taking strong inhibitors, the required washout period prior to starting olaparib is 2 weeks. For patients taking strong inducers, the required washout periods prior to starting olaparib in Part A are:

- Phenobarbitone, 5 weeks
- For any of the others, 4 weeks.

If the use of any potent inducers or inhibitors of CYP3A4 are considered necessary for the patient's safety and welfare during Part B, the investigator must contact the AstraZeneca Physician or their designated Medical Monitor. A decision to allow the patient to continue in the study will be made on a case-by-case basis.

Long term use of potent inducers and inhibitors of CYP3A4 should be avoided. If a decision is made to allow patients to use a potent inducer or inhibitor then they must be monitored carefully for any change in efficacy or safety of olaparib.

In vitro olaparib is a substrate for the efflux transporter Pgp. Clinical studies to evaluate the impact of known Pgp inhibitors and inducers have not been conducted. It is possible that olaparib may cause clinically relevant drug interactions with substrates of Pgp.

5.6.2.2 Effect of olaparib on other drugs

Olaparib can inhibit CYP3A4 and UGT1A1 in vitro. These findings suggest that olaparib has the potential to cause clinically significant interactions with other CYP3A4 substrates or UGT1A1 substrates in the liver or gastrointestinal tract. Therefore, caution should be exercised when substrates of CYP3A4 are combined with olaparib, in particular those with a narrow therapeutic margin (eg, simvastatin, cisapride, cyclosporine, ergot alkaloids, fentanyl, pimozide, sirolimus, tacrolimus and quetiapine). Substrates of UGT1A1 should also be given with caution in combination with olaparib (eg, irinotecan, nintedanib, ezetimibe, raltegravir or buprenorphine).

Induction of CYP1A2, 2B6 and 3A4 has been shown in vitro with CYP3A4 being most likely to be induced to a clinically relevant extent. The potential for olaparib to induce CYP2C9, CYP2C19 and Pgp is unknown. It cannot be excluded that olaparib upon co-administration may reduce the exposure to substrates of these metabolic enzymes and transport protein. The efficacy of hormonal contraceptives may be reduced if co administered with olaparib.

In vitro olaparib has been shown to be an inhibitor of Pgp, OATP1B1, OCT1, OCT2, OAT3, MATE1 and MATE2K and is a weak inhibitor of BRCP. It cannot be excluded that olaparib may increase the exposure to substrates of Pgp (eg, statins, digoxin, dabigatran, colchicine), OATP1B1 (eg, bosentan, glibenclamide, repaglinide, statins, and valsartan), OCT1 (eg, metformin), OCT2 (eg, serum creatinine), OAT3, MATE1 and MATE2K. In particular, caution should be exercised if olaparib is administered in combination with any statin.

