1. ACCEPTABLE BIRTH CONTROL METHODS

Olaparib is regarded as a compound with medium/high foetal risk.

Women of childbearing potential and their partners, who are sexually active, must agree to the use of 2 highly effective forms of contraception in combination [as listed below], throughout the period of taking study treatment and for at least 1 month after last dose of study drug(s), or they must totally/truly abstain from any form of sexual intercourse (see below).

Male patients and their partners, who are sexually active and of childbearing potential, must agree to the use of 2 highly effective forms of contraception in combination [as listed below], throughout the period of taking study treatment and for 3 months after last dose of study drug(s) due to the unknown effects of the study drug on the sperm, or they must totally/truly abstain from any form of sexual intercourse (see below). Male patients should not donate sperm throughout the period of taking study treatment and for 3 months following the last dose of study drug(s).

Acceptable Non-hormonal birth control methods include:

- Total sexual abstinence. Abstinence must continue for the total duration of study treatment and for at least 1 month after the last dose for women of childbearing potential and their partners and for 3 months after last dose for male patients. Periodic abstinence (eg, calendar ovulation, symptothermal post ovulation methods) and withdrawal are not acceptable methods of contraception.
- Vasectomised sexual partner PLUS male condom. With participant assurance that partner received post-vasectomy confirmation of azoospermia.
- Tubal occlusion PLUS male condom
- IUD PLUS male condom. Provided coils are copper-banded

Acceptable hormonal methods:

- Normal and low dose combined oral pills PLUS male condom
- Cerazette (desogestrel) PLUS male condom. Cerazette is currently the only highly efficacious progesterone based pill.
- Hormonal shot or injection (eg., Depo-Provera) PLUS male condom
- Etonogestrel implants (eg, Implanon, Norplant) PLUS male condom
- Norelgestromin / EE transdermal system PLUS male condom
- Intrauterine system [IUS] device (eg, levonorgestrel releasing IUS -Mirena®) PLUS male condom
- Intravaginal device (eg, EE and etonogestrel) PLUS male condom

Clinical Study Protocol Appendix G

Drug Substance	Olaparib (AZD2281, KU-0059436)
Study Code	D0816C00005
Edition Number	1.0
Date	03 June 2013

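### Hormonal contraception counts towards the two required highly effective forms for female patients with no caveat, although Section 5.6.2.2 says olaparib may weaken it

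*Protocol*

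**What the plan says.** Section 5.1 of the protocol sets the standard. Sexually active female patients of childbearing potential, with their partners, "must agree to the use of 2 highly effective forms of contraception in combination throughout the period of taking study treatment". This obligation lasts until at least 1 month after the last dose. The same paragraph says that "acceptable methods include barrier methods, implants, injectables, combined oral contraceptive methods", then adds some IUDs, abstinence and a vasectomised partner, and refers to Appendix F for details.

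Appendix F has a non-hormonal list and a hormonal list. The non-hormonal list includes "IUD PLUS male condom. Provided coils are copper-banded". The hormonal list has seven entries, from "Normal and low dose combined oral pills PLUS male condom" to an intravaginal device, and every one is paired with a male condom.

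Section 5.6.2.2, on the effect of olaparib on other drugs, says both "Olaparib can inhibit CYP3A4 and UGT1A1 in vitro" and "Induction of CYP1A2, 2B6 and 3A4 has been shown in vitro with CYP3A4 being most likely to be induced to a clinically relevant extent". The paragraph on induction ends with the warning "The efficacy of hormonal contraceptives may be reduced if co administered with olaparib". It does not say what a patient using such a method should do.

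**The concern.** The protocol asks for two highly effective forms and accepts a hormonal method as one of them. Elsewhere it says that the study drug may make that method less effective. Nothing in Section 5.1 or Appendix F brings the two statements together where the contraceptive is chosen. An investigator working from the Appendix F list could clear a woman for Part B on a hormonal method without meeting the warning.

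What is at stake is foetal exposure. Appendix F rates the foetal risk of olaparib as medium to high, and Section 1.1.2 reports effects on embryofetal survival and development at doses without significant maternal toxicity. Women of childbearing potential are eligible under inclusion criterion 12. Part B is where it matters most, because dosing is continuous: note b to Table 10 plans for up to an estimated 15 months in the study, and Section 3.1 allows treatment to go on after Part B ends. The single dose in Part A is a much smaller concern.

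**Working it through.** The plan gives no figure to reproduce, and no power or error-rate calculation bears on the point. The check sets the passages side by side.

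**Step 1: how many forms remain if the interaction occurs.** Appendix F has 7 hormonal and 4 non-hormonal entries, 11 in all. Section 5.6.2.2 treats hormonal contraceptives as one class, and so does this comparison.

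| Appendix F entries | Required combination | Forms the interaction would not affect |
|---|---|---|
| 7 hormonal entries | hormonal method + male condom | 1 (the condom) |
| 3 non-hormonal entries (vasectomised partner, tubal occlusion, copper-banded IUD) | non-hormonal method + male condom | 2 |
| 1 entry, total abstinence | stands alone | not affected |

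The condom accompanies the three non-hormonal methods as well. It is therefore the general second form and not an answer to the interaction. Two women can both comply fully with Appendix F and have different numbers of unaffected forms.

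**Step 2: whether another passage closes the gap.**

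- Section 5.1 has a pointer, "For restrictions regarding concomitant medications, please see Section 5.6", but it concerns concomitant medication in general. The contraception paragraph itself refers only to Appendix F.
- Section 5.6.2.2 advises caution with CYP3A4 substrates, UGT1A1 substrates and statins. The sentence on contraceptives carries no instruction.
- Section 5.6.7 bars hormonal therapy other than hormone replacement, but it sits among anti-cancer treatments. Since Appendix F expressly accepts hormonal contraception, Section 5.6.7 cannot be read as excluding it.
- Section 13.3.1 foresees that olaparib may have interfered with a contraceptive, but only to decide whether a pregnancy that has already occurred is an adverse event.
- The note to Table 6 limits Part B pregnancy tests to suspected pregnancy. Section 6.4.5 adds a baseline test. Neither sets routine testing on treatment, so prevention rests on the method chosen.

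None of these passages restricts or ranks the methods for a woman taking olaparib.

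**Step 3: who is affected.** The point concerns female patients of childbearing potential who enter Part B and use a hormonal method. Female partners of male patients do not take olaparib. The protocol gives no count of the women concerned and no basis for one: entry to Part B is optional, the target of at least 3 patients of each sex per group applies only if possible, and menopausal status and contraceptive use are not projected.

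**The case against.** The strongest case against is that the protocol already builds in redundancy. No hormonal method is accepted alone, and requiring two forms in combination is meant to cover the case where one of them weakens. The warning is only a possibility: it draws on in vitro induction, the same section also reports in vitro inhibition of CYP3A4, and no effect size is given. Section 5.1 does send the reader to Section 5.6, pregnancy tests are required at screening and before the Part A dose, and olaparib stops at once if a pregnancy occurs. On this view, choosing between a hormonal and a non-hormonal method, each with a condom, is a risk decision for the sponsor. Pushing patients with advanced cancer, some with hepatic impairment, towards an IUD or a procedure because of an unquantified possibility is a real burden.

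Much of this stands. It rules out a flat exclusion of hormonal methods, and any restriction on account of the single Part A dose alone. It does not remove the gap. The two-form rule asks for two highly effective forms, and redundancy that relies on one of them weakening falls short of that. The safeguards cited detect or manage a pregnancy; they do not guide the choice of method.

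A reader might infer that hormonal contraception fails under olaparib, or that women in the trial are unprotected. The documents support neither. The warning says only that efficacy may fall, and a condom is always required. Nor do they give any basis for ranking one hormonal method as safer than another.

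**Conclusion.** The point holds as an inconsistency within the protocol's safety provisions. Its accepted list can fall short of its own standard of two highly effective forms, for women in Part B who use a hormonal method, if the interaction that Section 5.6.2.2 describes as possible does occur. In that case one form, the condom, is unaffected instead of two.

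The conclusion depends on the interaction being real, which the protocol leaves open, and on at least one such woman entering Part B, which it does not establish. The number affected may be zero, and the size of any loss of efficacy is unknown. The pharmacokinetic objective, analysis sets, sample size and decision rule are not touched. It should be corrected because the possible harm is serious, the alternatives are already in Appendix F and the change is cheap.

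**What to change.** Add to the contraception paragraph of Section 5.1, and at the head of the hormonal list in Appendix F:

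> Olaparib may reduce the efficacy of hormonal contraceptives (see Section 5.6.2.2). Female patients of childbearing potential entering Part B should use one of the non-hormonal options listed here (copper-banded IUD, tubal occlusion or vasectomised partner, each plus male condom, or total abstinence). A hormonal method plus male condom is used only if no non-hormonal option is suitable, after documented counselling on the possible interaction. Hormonal options remain acceptable for female partners of male patients.

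The cost is an amendment to two places and matching site guidance. The downside is that a few female patients with advanced cancer may have to change or add a method. The provision for cases where no non-hormonal option is suitable keeps that burden in proportion to a risk that is possible but not quantified.
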